#### 5.2.2 Dosage adjustment

The criteria of dose suspension or reduction are as follows:

- Dose suspension and dose reduction can be carried out, only when the hematologic toxicity and non-hematological toxicity reach Grade 3 (special AEs such as hypertension, drug suspension or adjustment should be specified separately)
- > in non-hematological toxicity, subjects received active symptomatic treatment for subjects with

weight loss, nausea, vomiting, alopecia, fever with definite causes (such as infection), and elevated alkaline phosphatase (AKP) (Grade 3/4) without dose suspension and/or dose reduction.

➤ for hypertension AEs, antihypertensive drugs should be started and/or added when blood pressure is confirmed to be elevated (systolic blood pressure ≥ 140 mmHg or diastolic blood pressure ≥ 90 mmHg). If the blood pressure remains good (systolic blood pressure < 140 mmHg or diastolic blood pressure < 90 mmHg), the drug use can be continued. If systolic blood pressure ≥ 160 mmHg or diastolic blood pressure ≥ 100 mmHg still exists after the maximum dose of antihypertensive drug treatment, the drug administration should be interrupted; if the systolic blood pressure ≤ 150 mmHg and diastolic blood pressure ≤ 95 mmHg, and the subject has received the stable dose of antihypertensive drugs for at least 48 hours, the dosage can be reduced to 250mg.

#### 5.2.3 Dose interruptions

To ensure the drug intensity of the treatment for the subjects in the trial, the time of each suspension and the total time of suspension in each administration cycle should not exceed 2 weeks; the suspension time of each cycle should not exceed 2 times.

#### 5.2.4 Dose reduction

Dose adjustment is made at any time in each administration cycle. After the dose is reduced, it should not be brought back to the previous level. After the dose is adjusted to 250 mg q.d., continued dose adjustment is not allowed, including dose increase or decrease for any reason, but dose suspension is still allowed.

AE classification	NCI	Dose adjustment
		stop medication and continue to use the original dose when
Hematology AE	Grade 3	the AE $\leq$ Grade 2. If Grade 3 or above AEs occur again, the
		drug should be continued after a-dose reduction

Table 1 principle of dose adjustment of apatinib
--

	Grade 4	the drug is suspended, and the drug is continued after a-dose
		reduction and the AE recovered to $\leq$ Grade 2.
Non-hematological AE	Grade 3	The drug should be suspended until the AE $\leq$ Grade 1, and the
		drug should be continued with the original dose; if Grade 3 or
		above AEs occurs again, the drug should be continued after a-
		dose reduction.
	Grade 4	the drug is suspended, and the drug is continued after a-dose
		reduction and the AE recovered to $\leq$ Grade 1.

Note: the above evaluation is carried out according to NCI-CTCAE4.0

For subjects with gastrointestinal perforation, wound dehiscence, fistula, severe bleeding, nephrotic syndrome or hypertensive crisis, administration should be stopped permanently. Subjects with moderate to severe proteinuria or severe hypertension who need further diagnosis should stop using the drug temporarily.

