## 4.3 Exclusion Criteria

1. Histological subtypes of thyroid carcinoma other than differentiated type (such as medullary carcinoma, lymphoma, or sarcoma).

2. Subjects who have used VEGFR-TKI, such as vandetanib, cabozantinib, lenvatinib, sunitinib, sorafenib, etc. within 1 month before the first dose of study treatment.

3. Heart diseases that cannot be well controlled, such as: (1) cardiac insufficiency (grade 2 or above) according to the New York Heart Association (NYHA) standard, or cardiac color Doppler ultrasound examination: LVEF (left ventricular ejection fraction) < 50%; (2) unstable angina pectoris; (3) myocardial infarction within 1 year before the beginning of the study; (4) clinically significant supraventricular or ventricular arrhythmia, which need treatment or intervention: (5) QTc > 450ms (male); QTc > 470ms (female) (QTc interval is calculated by Fridericia formula); the average of three measurements is calculated with an interval of 2 minutes if QTc is abnormal; (6) subjects with hypertension who cannot be reduced to the normal range after anti-hypertension drug

treatment (SBP  $\geq$  140mmHg or DBP  $\geq$  90mmHg) (based on the average value of BP readings obtained from  $\geq$  2 measurements), the above parameters can be achieved through anti-hypertension treatment.

4. Factors affecting oral drug absorption (such as inability to swallow, nausea and vomiting, chronic diarrhea, and intestinal obstruction, etc.).

5. Subjects with the risk of gastrointestinal bleeding should not be included in the study, including:
(1) subjects with active peptic ulcer lesions and occult blood in stool (+ +); (2) subjects with a history of melena and hematemesis within 3 months.

6. Abnormal coagulation function (INR > 1.5, APTT >  $1.5 \times ULN$ ) with bleeding tendency.

7. Obvious hemoptysis within 2 months before screening, or the amount of hemoptysis reached half a teaspoon (2.5ml) or more every day.

8. Arteriovenous thrombosis events occurred within 12 months before screening, such as cerebrovascular accident (including transient ischemic attack, cerebral hemorrhage, cerebral infarction), deep vein thrombosis and pulmonary embolism, etc.

9. Received radiotherapy for thyroid carcinomas within 28 days before screening.

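### The permanent-stop list in 5.2.4 omits infarction and thromboembolism, so the only grade-based dosing rule for these events is Table 1, which resumes the drug on recovery

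*Protocol*

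**What the plan says.** All references are to the Protocol.

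- **Permanent stop (5.2.4, below Table 1).** "For subjects with gastrointestinal perforation, wound dehiscence, fistula, severe bleeding, nephrotic syndrome or hypertensive crisis, administration should be stopped permanently". Two of the six events get a second stop instruction elsewhere: hypertensive crisis in 6.2.2.2 and nephrotic syndrome in 6.2.4.
- **Table 1 (5.2.4), non-hematological events.** At Grade 3 the drug is held until Grade 1 or less, and then the "drug should be continued with the original dose; if Grade 3 or" higher recurs, it goes on at a reduced dose. At Grade 4, "the drug is suspended, and the drug is continued after a-dose" reduction once the event is at Grade 1 or less.
- **Threshold (5.2.2).** Holds and reductions are permitted only from Grade 3. Special events such as hypertension are to be dealt with separately.
- **Cap (5.2.3).** A hold may last at most 2 weeks, singly and in total per cycle. No consequence is stated if it runs longer.
- **Entry bars (4.3).** Item 3 excludes "myocardial infarction within 1 year before the beginning of the study". Item 8 excludes "Arteriovenous thrombosis events occurred within 12 months before screening, such as cerebrovascular accident", and the rest of its list of examples reads "including transient ischemic attack, cerebral hemorrhage, cerebral infarction), deep vein thrombosis and pulmonary embolism".
- **General stops.** Sections 3.1 and 5.1.2 let the investigator stop treatment. Section 4.5 ends treatment for toxicity that persists after dose adjustment, and has a catch-all. Section 5.2.1 allows discontinuation or reduction from Grade 3.

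**The concern.** Apatinib is a VEGFR inhibitor, and the protocol treats a recent infarction, stroke, embolism or deep vein thrombosis as serious enough to keep a patient out for a year. If the same event occurs on treatment, no section names a stop for it. The site is left with Table 1, whose written course after a Grade 3 or 4 non-hematological event is to hold, wait for recovery and continue.

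At stake is participant safety. A site following the dosing table would put a subject back on drug after a recovered infarction or pulmonary embolism, and sites using their own judgment could act differently from one another. The protocol writes a mandatory stop where it wants one, so a site may read the absence of these events from the list as deliberate.

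**Working it through.** No arithmetic beyond counting applies, and there is no stated figure to reproduce. The check sets the sections side by side. Cerebral infarction and TIA are counted as one event type.

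**1. Is any of the events on the stop list?** The list has six entries: gastrointestinal perforation, wound dehiscence, fistula, severe bleeding, nephrotic syndrome and hypertensive crisis. Overlap with the four event types: 0 of 4.

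**2. Does another section name a stop?** Sections 6.2.1 to 6.2.5 cover hand-foot skin reaction, hypertension, gastrointestinal bleeding, proteinuria and thyroid function. None deals with cardiac ischemia or thromboembolism. There is one partial exception: 6.2.2.2 counts cerebral infarction among the organ damage that makes a hypertensive emergency (diastolic pressure above 120 mmHg), and a hypertensive crisis requires an immediate stop.

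**3. What does Table 1 then prescribe?** The starting dose is 500 mg and the only reduced level is 250 mg (5.2.1).

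| Non-hematological event | Hold until | Then |
|---|---|---|
| Grade 3, first | Grade 1 or less | continue at 500 mg |
| Grade 3 or above, again | not restated | continue at 250 mg |
| Grade 4 | Grade 1 or less | continue at 250 mg |

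Table 1 has two non-hematological rows, Grade 3 and Grade 4. Both end in continuation and neither in a stop. That holds however CTCAE 4.0 grades these events, which the protocol does not show. Below Grade 3, the condition in 5.2.2 leaves no written basis even for a temporary hold, for example after a lower-grade TIA or deep vein thrombosis.

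**4. How do the entry bars compare with the stop list?**

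| Event | Past-period bar in 4.3 | Permanent stop in 5.2.4 |
|---|---|---|
| Myocardial infarction | 1 year (item 3) | no |
| Cerebral infarction, TIA | 12 months (item 8) | no, unless part of a hypertensive crisis |
| Pulmonary embolism, deep vein thrombosis | 12 months (item 8) | no |
| Cerebral hemorrhage | 12 months (item 8) | plausibly, as severe bleeding |
| Intestinal perforation | 28 days (item 10) | yes |
| Gastrointestinal bleeding: "subjects with a history of melena and hematemesis within 3 months" | 3 months (item 5) | if severe |
| "Obvious hemoptysis within 2 months before screening" | 2 months (item 7) | if severe |
| Ulcer, intestinal obstruction | 28 days (item 10) | no |
| Wound dehiscence, fistula, nephrotic syndrome, hypertensive crisis | none by name | yes |

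The events with the longest bars are the ones missing from the stop list. The match is loose in both directions, however: ulcer and obstruction are barred but not listed, and four of the six listed events have no past-period bar by name. The comparison supports the concern but does not establish a rule that the protocol breaks.

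**5. Do the general clauses close the gap?** They permit a stop but require none for these events. The toxicity criterion in 4.5 applies after dose adjustment, so it presupposes re-dosing. Section 5.2.1 mentions discontinuation, then asks for suspension first for the sake of consistency. The 2-week cap limits when resumption can happen but does not say that the drug is stopped when the cap is passed.

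**The case against.** The strongest reply is that no investigator is forced to re-dose. Sections 3.1, 4.5 and 5.1.2 give written authority to stop, 5.2.1 allows discontinuation from Grade 3, and Table 1 is headed as a principle. This stands. A reader might infer that Table 1 is the only written dosing rule for these events, or that resumption is compelled; the documents support neither. Table 1 is the only *grade-based* rule that reaches them, and discretion stands beside it.

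A reader might also infer that the one-year entry bars and the stop list contradict each other. They do not. An entry bar does not by itself imply a permanent stop, and the list was evidently not built from the bars.

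The practical reach is also unknown. Whether an event reaches Grade 3, and whether it falls to Grade 1 or less within 2 weeks, decides if Table 1 ever leads to a restart, and the protocol shows neither. It gives no thromboembolic rate; the earlier single-arm trial in 1.3 lists hand-foot syndrome, hypertension and hypocalcemia as the most common Grade 3 events. This limits any claim about frequency, but not the point that the written default is wrong when such an event occurs.

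Other safeguards make unreviewed re-dosing less likely: cardiac enzymes and Doppler ultrasound for chest symptoms (7.3, 7.4), 24-hour reporting of serious events (9.5), emergency unblinding (9.6) and committee review of safety data at the interim (10.4). None of them sets a dosing rule.

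**Conclusion.** The point holds as a gap in the dosing rules. None of the four event types is on the six-event stop list. Both non-hematological rows of Table 1 continue the drug after recovery, and below Grade 3 there is no basis for a hold. A stop is left to general investigator discretion, except for cerebral infarction within a hypertensive crisis. Because Table 1 states a course of action, this is an unsafe written default and not merely a silence.

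It should be corrected on patient-safety grounds. It changes no sample size, power or alpha, and no incidence is assumed. The conclusion rests on reading Table 1 as applying to every non-hematological event without a rule of its own, which is how 5.2.2 and 5.2.4 are laid out.

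**What to change.** 1. In the permanent-stop sentence of 5.2.4, add myocardial infarction, cerebral infarction and transient ischemic attack.
2. After it, add a short rule for pulmonary embolism and deep vein thrombosis: suspend study drug at any grade; resumption under Table 1 does not apply automatically; stop permanently if the event is life-threatening; otherwise restart only on a documented investigator decision that the subject is clinically stable, within the 2-week limit of 5.2.3.
3. State that both additions take precedence over Table 1 and over the Grade 3 condition of 5.2.2.

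The restart conditions for venous events are a clinical proposal, not something derived from the protocol. The sponsor may set others, provided that recovery in grade alone no longer triggers resumption.

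The cost is a few words and one short paragraph in an amendment, a notice to sites, and possibly a few more permanent discontinuations in either arm. Follow-up for progression-free survival is kept: under 4.5, stopping treatment is not leaving the study, and 7.5 continues imaging every 2 months until progression or another anti-tumor therapy.

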# 6 Concomitant medication and common AEs

# 6.1 Drugs prohibited or used with caution during the trial

#### 6.1.1 Drugs interfering with liver P450 enzyme

Apatinib had strong inhibitory effect on CYP3A4, YP2C9 and CYP2C19 (IC50 <  $0.5 \mu$ M). Omeprazole should be banned during treatment (except for the cases that must be used due to serious AEs). The inducers (dexamethasone, rifampicin, and phenobarbital) and inhibitors (itraconazole, erythromycin and clarithromycin) of CYP3A4, substrates of CYP3A4 (simvastatin, cyclosporin and piperazine, etc.) and other drugs metabolized by CYP3A4 (such as benzodiazepines, dihydropyridines, calcium antagonists and HMG-CoA reductase inhibitors) should be used with caution. Careful use of CYP2C9 substrates (diclofenac, phenytoin, piroxicam, S-warfarin and tolbutamide) and CYP2C19 substrates (diazepam, imipramine, lansoprazole and S-mephenytoin).

#### 6.1.2 Drugs causing prolongation of cardiac QT interval

Since protein tyrosine kinase drugs have side effects in clinical, such as prolonging QT interval, it is required to use drugs that can prolong QT interval carefully, including antibiotics (Fluoroquinolones: sparfloxacin, gatifloxacin, levofloxacin, moxifloxacin, ofloxacin, ciprofloxacin, etc.; Macrocyclic lipids: erythromycin, clarithromycin, talimycin, azithromycin, roxithromycin, metronidazole, etc.), anti-angina drugs (ranolazine, ivabradine, etc.), anti-arrhythmic drugs (quinidine, procaine amine, propylamine, flucarni, propafenone, amiodarone, dronedarone, sotalol, dofetilide, ibutilide, etc.), anti-psychotic drugs (risperidone, flufenazine, droperidol, haloperidol, tiridazine, pimozide, olanzapine, clozapine, etc.). Anti-fungal drugs (voriconazole, posaconazole, etc.), anti-malarial drugs (mefloquine, chloroquine, etc.), gastrointestinal drugs (antiemetics: ondansetron, granisetron, droasetron, droperidol, (0.625-1.25 mg may be a safe dose)), hydroxyzine; gastrointestinal motility drugs: cisapride, domperidone, metoclopramide, etc.), antihistamines (terfenadine, astemizole, hydroxyzine, etc.) and anti-depressants (amitriptyline, imipramine, clomipramine, dutiapine, doxepin, etc.) and other drugs.

# 6.1.3 Traditional Chinese medicine and immune preparations with anti-cancer effect

The use of modern Chinese medicine preparations and immunomodulators with indications for the treatment of thyroid cancer approved by CFDA is prohibited during the trial.

#### 6.1.4 Drugs that can be combined used during the trial

All kinds of clinical AE (such as hypertension, hand foot skin reaction, liver, and kidney function damage, etc.) should be treated according to the judgment of clinicians. All drugs used in combination should be recorded in case report form (CRF) in strict accordance with GCP.

# 6.2 Symptomatic treatment suggestions for common AEs

#### 6.2.1 Hand foot skin reaction

Hand foot skin reaction (HFSR): it is a kind of skin toxicity, which is more obvious in compression or stress area when it occurs. HFSR may appear in subjects with tumor during chemotherapy or molecular targeted therapy. HFSR is characterized by numbness, dullness, paresthesia, tingling, no pain or pain, skin swelling, or erythema, desquamation, chapping, sclerosing blisters and severe pain.

#### 6.2.1.1 HFSR classification

Grade 1: numbness/dullness/paresthesia of hand and/or foot, painless swelling, or erythema and/or discomfort that does not affect normal activity.

Grade 2: painful erythema and swelling of hand and/or foot and/or discomfort affecting the patient's daily activities.

Grade 3: wet desquamation of hand and/or foot, ulcers, blisters, or severe pain and/or severe discomfort that prevents the patient from working or performing daily activities. Severe pain and loss of skin function is rare.

#### 6.2.1.2 Symptomatic treatment and management of HFSR

Take some necessary symptomatic supportive treatments, including strengthening skin care, keeping skin clean, avoiding secondary infection, avoiding pressure or friction, using moisturizing cream or lubricant, topical use of urea or corticosteroid emulsion or lubricant, and locally using antifungal or antibiotic therapy.

#### 6.2.2 Hypertension

#### 6.2.2.1 Suggestions for drug-related hypertension treatment

- Monitoring and treatment of hypertension: blood pressure monitoring should be conducted every week in the first six weeks of targeted drug treatment. Once hypertension occurs, the following standard treatment drugs can be given angiotensin-II receptor blocker (ARB), angiotensin converting enzyme inhibitor (ACEI), β-receptor blocker and diuretic, or combination of the above drugs.
- > Optimization of drug selection (non-liver metabolism drugs):

1) Valsartan (Devon),  $80 \sim 320$ mg q.d.

2) Atenolol,  $50 \sim 100$  mg q.d.

3) HCTZ, 12.5~100mg q.d.

4) Telmisartan,  $20 \sim 80$ mg q.d.

5) For those whose blood pressure is difficult to control: amlodipine,  $2.5 \sim 10$ mg q.d.

#### 6.2.2.2 Clinical stages of hypertension and routine treatment

- Prehypertension: (120-139/80-89 mmHg, or systolic blood pressure 120-139 mmHg): there is no indication of using antihypertensive drugs, only blood pressure is monitored
- Grade 1 hypertension: (140-159/90-99 mmHg, or systolic blood pressure is 140-159 mmHg): use drugs to reduce blood pressure and monitor blood pressure at the same time; most of them use thiazide diuretics, but also consider using ARB, ACEI, β-receptor blockers and calcium channel blockers; continue to take apatinib, and two anti-hypertensive drugs can be considered if the blood pressure is not ideal.
- ➤ Grade 2 hypertension: (160-179/100-109 mmHg, or systolic blood pressure ≥ 160-179 mmHg): combined use of two drugs (usually thiazide diuretics and ARB or ACEI or β-receptor blockers or calcium channel blockers); monitor blood pressure.
- Grade 3 hypertension: (≥180/110 mmHg, or systolic blood pressure≥180 mmHg): combined use of two drugs (usually thiazide diuretics and ARB or ACEI or β-receptor blockers or calcium channel blockers); closely monitor blood pressure; assess other risk factors (such as target organ damage, diabetes and other clinical symptoms), and take corresponding measures
- Hypertension crisis: refers to a serious clinical state in which blood pressure is excessively elevated and diastolic blood pressure exceeds 16.0-17.3 kPa (120-130 mmHg). At present, there is no unified classification at home and abroad. Recently, it can be divided into two types from the perspective of clinical treatment: (1) Hypertension emergencies: diastolic blood pressure>16.0 kPa (120 mmHg), accompanied by acute or progressive target organ damage, such as cerebral infarction, intracranial or subarachnoid hemorrhage, hypertensive

encephalopathy, and so on. Rapidly progressive hypertension based on chronic essential hypertension is the most common (about 40%~50%). (2) Hypertension urgencies: diastolic blood pressure>16.0 kPa (120 mmHg) without or with only slight organ damage; sodium nitroprusside or nifedipine is used to reduce blood pressure rapidly; diazepam and phenobarbital are used to stop convulsion; furosemide and mannitol are used to reduce intracranial pressure.

Note: in case of hypertension crisis, the use of apatinib should be stopped immediately and the patient should be withdrawn from the clinical trial.

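### Sections 6.2.2.2 and 5.2.2 give opposite instructions for a raised diastolic pressure, and 5.2.2 classes the same reading as both elevated and good

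*Protocol*

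**What the plan says.** **Section 6.2.2.2** sorts readings into prehypertension, Grades 1 to 3 and hypertension crisis.

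- Prehypertension and its management: "120-139/80-89 mmHg, or systolic blood pressure 120-139 mmHg): there is no indication of using antihypertensive drugs, only blood pressure is monitored".
- Grade 1: "140-159/90-99 mmHg, or systolic blood pressure is 140-159 mmHg): use drugs to reduce blood pressure and monitor blood pressure at the same time". Apatinib continues.
- Grade 2: "160-179/100-109 mmHg, or systolic blood pressure ≥ 160-179 mmHg): combined use of two drugs".
- Grade 3 follows the same pattern, from 180/110 mmHg or from systolic 180 mmHg alone.
- Crisis is the only class defined by diastolic pressure (above 120 mmHg). Apatinib is stopped and the subject withdrawn.

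**Section 5.2.2** sets the hypertension rules that bear on dosing.

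- Antihypertensives should be started or added when pressure is confirmed as elevated: "systolic blood pressure ≥ 140 mmHg or diastolic blood pressure ≥ 90 mmHg".
- Study drug may continue on this condition: "If the blood pressure remains good (systolic blood pressure < 140 mmHg or diastolic blood pressure < 90 mmHg".
- Study drug should be interrupted if systolic is still at least 160 or diastolic at least 100 mmHg after maximum antihypertensive treatment.
- Dosing at 250 mg may follow when systolic is at most 150 **and** diastolic at most 95 mmHg, with a stable antihypertensive dose for at least 48 hours.

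**The concern.** Prehypertension and Grades 1 to 3 each have a criterion that systolic pressure alone can meet, and none has a matching one for diastolic pressure alone. A subject with systolic 120-139 and diastolic 90 or more can therefore be placed in a class for which drug treatment is said not to be indicated, while 5.2.2 tells the investigator to treat.

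Separately, the definition of good pressure in 5.2.2 overlaps with its own definition of elevated pressure, so one reading can meet the condition for continuing study drug and the condition for interrupting it.

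Hypertension is an expected toxicity. Section 1.3 lists it among the most common Grade 3 events (30%, from a single-arm study of ten patients at 750 mg daily). Several centres will apply these rules, and the text should give one answer per reading. At stake is consistent safety management, not the efficacy comparison.

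**Working it through.** The plan has no figure to reproduce here. The check applies the written rules to sample readings. S is systolic and D diastolic pressure in mmHg.

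**Rules as written**

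- 6.2.2.2, prehypertension: (S 120-139 / D 80-89) or S 120-139
- 6.2.2.2, Grade 1: (S 140-159 / D 90-99) or S 140-159
- 6.2.2.2, Grade 2: (S 160-179 / D 100-109) or S 160-179
- 6.2.2.2, Grade 3: (S ≥ 180 / D ≥ 110) or S ≥ 180
- 5.2.2, elevated: S ≥ 140 or D ≥ 90
- 5.2.2, good: S < 140 or D < 90
- 5.2.2, interruption limit, on maximum antihypertensive treatment: S ≥ 160 or D ≥ 100

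The slash is not defined, so it was read both as *and* (both values in range) and as *or* (either value suffices).

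| Reading | 6.2.2.2, slash = and | 6.2.2.2, slash = or | 5.2.2 elevated | 5.2.2 good, as written | Good with *and* | At interruption limit |
|---|---|---|---|---|---|---|
| 135/85 | Prehypertension | Prehypertension | no | yes | yes | no |
| 135/95 | Prehypertension | Prehypertension and Grade 1 | yes | yes | no | no |
| 135/105 | Prehypertension | Prehypertension and Grade 2 | yes | yes | no | yes |
| 145/85 | Grade 1 | Prehypertension and Grade 1 | yes | yes | no | no |
| 145/95 | Grade 1 | Grade 1 | yes | no | no | no |

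**Step 1: 6.2.2.2 against 5.2.2.** With the slash as *and*, prehypertension is the only class that fits 135/95 and 135/105, so 6.2.2.2 says monitor only. Section 5.2.2 says treat, because 95 ≥ 90 and 105 ≥ 90. With the slash as *or*, each reading falls in two classes with opposite treatment advice and nothing ranks them. The opposite instruction from 6.2.2.2 under the *and* reading is confined to systolic 120-139 with diastolic from 90 up to the crisis level.

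**Step 2: 5.2.2 against itself.** The opposite of (S ≥ 140 or D ≥ 90) is (S < 140 **and** D < 90). As written, good fails only when both values are raised. Elevated and good therefore overlap exactly when one of the two values is raised, as at 135/95, 135/105 and 145/85. The first and last rows are controls: 135/85 is only good and 145/95 only elevated.

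**Step 3: consequence for dosing.** Take 135/105 on maximum antihypertensive treatment. It is good because 135 < 140, so study drug can continue; it is at the interruption limit because 105 ≥ 100, so study drug should be interrupted. A reading of 165/85 does the same from the systolic side (85 < 90, but 165 ≥ 160).

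**Step 4: what was intended.** The 250 mg rule in 5.2.2 joins its two limits with *and*. Exclusion criterion 3(6) in section 4.3 treats systolic ≥ 140 or diastolic ≥ 90 as outside the normal range. Both point to *and* as the intended word in the definition of good.

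**The case against.** The strongest reply is that the treatment threshold in 5.2.2 is firm, uses a correct either-value rule and would govern in practice. Section 6.2 is headed "Symptomatic treatment suggestions for common AEs", and section 6.1.4 says that adverse events such as hypertension "should be treated according to the judgment of clinicians". If either half of the slash pair suffices, 135/95 also meets Grade 1, whose advice is to treat, so 6.2.2.2 does not then withhold treatment outright. The list does act on diastolic pressure at crisis level. *Good* governs only whether study drug continues; it does not tell anyone to withhold antihypertensives. For 135/95 or 150/85 the correction alters no dosing action, because neither reaches the interruption limit. The Grade 3 hypertension in section 1.3 was seen at 750 mg in ten patients, while this trial starts at 500 mg. Subjects measure their own pressure at least three days a week in the first two cycles and daily once it is abnormal.

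Most of this stands and limits the weight. A site would probably follow 5.2.2, but the protocol states no precedence. The claim that 6.2.2.2 withholds treatment outright needs the slash read as *and*; under the other reading the text gives two answers. The reply that no dosing decision is touched fails for 135/105 and 165/85 on maximum treatment, where both conditions lie within 5.2.2 itself. A reader may fairly let the specific interruption rule override the permissive one, but has to supply that ranking.

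**Conclusion.** The concern holds, as a minor one. Two wording faults are established from the text alone:

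- All four of prehypertension and Grades 1 to 3 have a stand-alone systolic criterion, and none states a stand-alone diastolic one. For systolic 120-139 with diastolic 90 or more, 6.2.2.2 therefore conflicts with 5.2.2 or gives two answers, depending on how the slash is read.
- Within 5.2.2, every reading with exactly one raised value is both elevated and good. On maximum antihypertensive treatment, some of these readings meet the conditions both for continuing and for interrupting study drug.

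No number of affected subjects can be given, because the document reports no rate of isolated diastolic elevation at 500 mg. Frequent pressure checks and clinical judgment limit the likely harm. The primary analysis, sample size and alpha are untouched.

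**What to change.** 1. In 6.2.2.2, define each class by systolic **and/or** diastolic range, and state that the higher class rules. Then 135/95 is Grade 1, 135/105 is Grade 2 and 145/85 is Grade 1; all three are treated, in line with 5.2.2.
2. State that the 5.2.2 thresholds govern antihypertensive treatment and study-drug dosing where the two sections differ.
3. In 5.2.2, define good pressure as systolic < 140 **and** diastolic < 90 mmHg, the exact complement of the elevated threshold.
4. Add a clause that study drug continues while antihypertensives are adjusted, unless the interruption limit is met. Otherwise the corrected definition leaves 5.2.2 silent on continuing at, say, 135/95. Grade 1 in 6.2.2.2 already says to continue.

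The cost is a wording correction in two sections and a memo to sites, with no extra visits, tests or subjects.
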